3.2. Protocol Violations

At the discretion of the sponsor, major protocol violations as determined by a review of the data prior to unblinding of the study results and the conduct of statistical analyses may result in the removal of a subject’s data from the MK/PD Populations. The Sponsor, or designee, will be responsible for producing the final protocol violation file (formatted as a Microsoft Excel file), in collaboration with the CRO (Cytel) and the data monitoring group as applicable; this file will include a description of the protocol violation, and clearly identify whether or not this violation

warrants exclusion from either the MK or PD Population. This file will be finalized prior to hard database lock.

Major protocol violations are defined as those deviations from the protocol that are likely to have an impact on the subject's rights, safety, well-being, and/or on the validity of the data for analysis regarding primary and secondary outcomes. The Biostatistician may consider some data to be invalid for analysis, which would be defined as a major deviation and would lead to exclusion of that subject from the relevant population.

All protocol violations will be presented in the data listings.

4. STATISTICAL METHODS

4.1. Sample Size Justification

Part 1: The sample size for the sentinel cohort (6 subjects) is primarily designed for empirical evaluation of safety and tolerability in subjects with cirrhosis.

Part 2: A sample of 16 subjects must complete all 3 ammonia AUC intervals (baseline, Day 5, and Day 6) to detect a 20% reduction in average daily ammonia ($AUC_{0-24}/24$, from a baseline of 70 $\mu\text{mol/L}$) with an approximate significance level of 10% and an approximate power of 90%. Significance and power are approximate based on the assumptions below. The number of subjects assumes that the SD of spot ammonia is 9 $\mu\text{mol/L}$, approximately half of the variance is between subject, and that the SD for average daily ammonia is as little as half that of spot ammonia. The spot ammonia SD is based on a weighted average of SD observed in a prior study of ammonia lowering in a similar population. The variability of AUC may be 50% lower than spot ammonia based on the FDA summary basis of approval for glycerol phenylbutyrate for urea cycle disorders.

4.2. General Statistical Methods and Data Handling

4.2.1. General Methods

All output will be incorporated into Microsoft Excel or Word files, sorted and labeled according to the International Conference on Harmonisation (ICH) recommendations, and formatted to the appropriate page size(s).

Tabulations will be produced for appropriate demographic, baseline, PD, microbiotic-kinetic and safety parameters. For categorical variables, summary tabulations of the number and percentage within each category (with a category for missing data) of the parameter will be presented. For continuous variables, the mean, standard deviation, arithmetic percent coefficient of variation (%CV), geometric mean (geo mean), geometric percent coefficient of variation (geo %CV), median, minimum and maximum values will be presented. For discrete numeric variables (e.g. T_{lag}), the median, minimum, and maximum will be presented.

Formal statistical hypothesis testing will be performed on all primary, secondary [REDACTED] [REDACTED] endpoints with all tests conducted at the 1-sided, 0.10 level of significance. Summary statistics will be presented, as well as confidence intervals on selected parameters, as described in the sections below.

Baseline will be defined as the last scheduled measurement prior to the first IP administration (i.e., pre-dose). If a sequence of baseline measurements is taken pre-dose on the same day, time-matched baseline will be used. If multiple measurements are included within a baseline measurement (e.g., repeated measures at the same nominal time), the arithmetic mean of the multiple samples will be considered the baseline. Unscheduled measurements will only be used as baseline upon consultation with the Sponsor.

For each local laboratory where normal reference range of ammonia has not been locally adequately validated, the normal reference range of ammonia will be defined based on approximately 30 healthy volunteers devoid of any chronic or acute medical conditions and medications with normal liver enzymes. Ammonia sampling, sample processing and analysis will be performed as defined in the SYNBI020-CP-002 protocol and lab manual. The 95th percentile will be used as ULN. Outliers based on visual inspection may be excluded on a case-

by-case basis, and if any outliers are excluded, will be reported in the Changes to Planned Analysis section of the CSR with appropriate notes added to tables and figures where outliers have been excluded.

4.2.1.1. Handling of Values below the Quantifiable Limit (BQL)

Results for endogenous compounds below the quantifiable limit (BQL) will be set to $\frac{1}{2}$ the lower limit of quantification (LLOQ).

Results for exogenous compounds (other than SYNBI020) BQL will be set to zero.

For SYNBI020 fecal copy number, BQL before the first quantifiable measurement will be set to 0 for calculations; BQL between two quantifiable measurements will be set to $\frac{1}{2}$ LLOQ; and BQL after the last quantifiable measurement will be set to 0 for calculations. For semi-logarithmic plotting, SYNBI020 fecal copy number BQL will be set to $\frac{1}{2}$ LLOQ for all measurements.

4.2.2. Computing Environment

All descriptive statistical analyses will be performed using SAS statistical software (Version 9.4) or R (Version 3.4.0 or greater), unless otherwise noted. Medical history and AEs will be coding using the Medical Dictionary for Regulatory Activities (MedDRA) version 20.1, and the severity of AEs and laboratory abnormalities will be graded using the NCI CTCAE, version 4.03. Concomitant medications will be coded using World Health Organization (WHO) Drug Version 10DEC01DDE.

4.2.3. Methods of Pooling Data

Not applicable to the present study.

4.2.4. Adjustments for Covariates

No formal statistical analysis that adjusts for possible covariate effects is planned.

4.2.5. Multiple Comparisons/Multiplicity

Multiplicity will be addressed via the Haybittle-Peto stopping boundary method for group sequential designs.

First, the IA will be evaluated against the efficacy p-value of 0.01.

The overall type I error will be fixed at $\alpha = 0.10$, allowing for unequal p-value boundaries at the two looks (IA and final). Further details will be provided in Section 4.6.

4.2.6. Subpopulations

The following subpopulations will be explored for the primary and key secondary endpoints, provided the sample size is adequate for analysis:

- Ammonia level: subjects with ammonia > 1.5 times ULN versus subjects with ammonia ≤ 1.5 times ULN
- Proton pump inhibitor (PPI) use: subjects already on PPI versus subjects given ranitidine
- Hepatitis status: subjects with a history of Hepatitis B/C versus subjects without a history of Hepatitis B/C

If subgroup analyses for the primary endpoint indicate important subgroup-by-treatment interactions, then further exploratory analyses on subgroups and other endpoints may be taken.

4.2.7. Withdrawals, Dropouts, Loss to Follow-up

Subjects who withdrew from the study may be replaced as defined in section 10.5 of the Protocol (Determination of Sample Size).

4.2.8. Missing, Unused, and Spurious Data

In general, there will be no substitutions made to accommodate missing data points. All data recorded on the case report forms (CRFs) will be included in data listings that will accompany the CSR.

If the start date of an AE is partially or completely missing, the date will be compared as far as possible with the date of the start of administration of study drug. The AE will be assumed to be treatment-emergent if it cannot be definitively shown that the AE did not occur or worsen during the treatment-emergent period (worst case approach).

The following general rules will be used:

- If the start date is complete, an AE will only be excluded as being treatment-emergent if the start date is before the date of first study drug administration or if the stop date is before first study drug administration.
- If the start day is missing but the start month and year are complete, an AE will only be excluded as being treatment-emergent if the start month/year is before the month/year of first study drug administration or if the stop month/year is before first study drug administration.
- If the start day and month are missing but the start year is complete, an AE will only be excluded as being treatment-emergent if the start year is before the year of first study drug administration or if the stop year is before the year of first study drug administration.

If the start date is completely missing, an AE will be considered treatment-emergent unless the stop date is before first study drug administration.

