4.6.1. Adverse Events

AEs will be coded using MedDRA and severity will be evaluated using the NCI CTCAE version 4.03. These will be displayed in tables and listings using System/Organ/Class (SOC) and Preferred Term (PT). AEs will also be presented by maximum severity.

AEs will be recorded from the time a subject signs informed consent through the safety follow-up period. Analyses will focus on any AE recorded, as well as treatment-emergent AEs (TEAEs), which are those events that have occurred after the start of the study drug.

AEs are summarized by subject incidence rates, therefore, in some tabulations, a subject contributes only once to the count for a given AE (SOC or PT). Several tabulations also show the total number of events, where a subject can contribute more than once.

The number and percentage of subjects, along with total number of events, with any AE, any TEAE, any TEAE assessed by the Investigator as related to treatment (definite, probable, or possible relationship), any AE resulting in discontinuation of study dosing and with any SAE will be summarized by treatment group and overall. In these tabulations, each subject will contribute only once (i.e., the most related occurrence or the most intense occurrence) to each of the incidence rates in the descriptive analysis, regardless of the number of episodes.

Tabulations will also be presented by MedDRA SOC and PT for the following: all TEAEs, related TEAEs, TEAEs by severity and TEAEs leading to permanent study drug withdrawal.

No formal hypothesis-testing analysis of AE incidence rates will be performed.

All AEs occurring on study will be listed in subject data listings.

By-subject listings also will be provided for the following: subject deaths; SAEs; AEs leading to withdrawal and Grade 3 or 4 AEs, and narratives will be shown for these.

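### SAP 4.2.8: two partial-date rules can class an adverse event with a known pre-dose stop date as treatment-emergent (minor; descriptive TEAE tables only)

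*SAP*

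**What the plan says.** SAP 4.2.8 opens with a principle for AEs whose start date is partly or wholly missing: "the date will be compared as far as possible with the date of the start of administration of study drug". Such an AE is then assumed treatment-emergent if "it cannot be definitively shown that the AE did not occur or worsen during the treatment-emergent period (worst case approach"). Four rules follow, introduced by "The following general rules will be used". They are numbered here in the order in which they appear.

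- **Rule 1, start date complete.** The AE is excluded if "the start date is before the date of first study drug administration or if the stop date is before first study drug administration".
- **Rule 2, start day missing.** The AE is excluded only if the start month/year precedes that of first dosing, "or if the stop month/year is before first study drug administration".
- **Rule 3, start day and month missing.** The AE is excluded only if the start year precedes the dosing year, "or if the stop year is before the year of first study drug administration".
- **Rule 4, start date wholly missing.** Here "an AE will be considered treatment-emergent unless the stop date is before first study drug administration".

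SAP 4.6.1 describes treatment-emergent AEs (TEAEs) with the words "which are those events that have occurred after the start of the study drug". It reports all AEs as well as TEAEs, bases its tabulations by system organ class and preferred term on TEAEs, and plans no hypothesis test of AE rates.

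**The concern.** A complete stop date before the first dose is definitive evidence that the event was over before treatment began. Rules 1 and 4 use that evidence. Rule 3 reduces the stop date to its year, and rule 2 reduces it to its month and year. Because both allow exclusion only on those tests, a programmer who follows the text has no other route to exclusion.

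The result is not monotone in the information available. An AE with no start date at all is correctly excluded on its stop date. The same AE with a start year, or with a start month in the dosing month, is counted as treatment-emergent.

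AEs are recorded from informed consent, so pre-dose events will be in the database. At stake is whether the TEAE tables hold only events that could have occurred on SYNB1020 or placebo. The arms are small enough for one event to be visible in a percentage.

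**Working it through.** The plan gives no figure for this point, so there is none to reproduce. The check applies the four rules literally.

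**Step 1. Worked dates.** First dose 20 September; the stop date is complete and before dosing.

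| Rule | Start date | Stop test | Start 3 Sep, stop 10 Sep | Start 3 Aug, stop 10 Aug |
|---|---|---|---|---|
| 1 | complete | full date | not TEAE | not TEAE |
| 2 | day missing | month/year | **TEAE** | not TEAE |
| 3 | day and month missing | year | **TEAE** | **TEAE** |
| 4 | wholly missing | full date | not TEAE | not TEAE |

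None of these events overlaps dosing, so every TEAE entry is wrong under the section's principle and under 4.6.1.

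**Step 2. Share misclassified, given the missing-date pattern.** Inputs:

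- Pre-dose window W = 50 days (45 days of screening in Protocol 4.5.2 plus 5 run-in days) or W = 35 days (30 days in SAP 4.2.9 plus 5). The two documents differ on screening length, so both are shown.
- Assumptions: the AE starts a days and stops b days before dosing, with all pairs 1 ≤ b ≤ a ≤ W equally likely; dosing dates are spread evenly over a 365-day year.
- Number of pairs = W(W+1)/2, which is 1,275 for W = 50 and 630 for W = 35.

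*Rule 2* goes wrong when the start, and hence the stop, falls in the dosing month. For dosing on day d of the month this is (d−1)d/2 pairs. Summed over a month of L days it is (L+1)L(L−1)/6: 4,960 for 31 days, 4,495 for 30 and 3,654 for 28.

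- Year total: 7×4,960 + 4×4,495 + 3,654 = 56,354. Per dosing date: 56,354/365 = 154.4.
- W = 50: 154.4/1,275 = **12.1%**. W = 35: 154.4/630 = **24.5%**.

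*Rule 3* goes wrong when the start falls in the dosing year. For the first W dosing dates of the year the pairs sum to (W+1)W(W−1)/6. For the other 365−W dates all pairs count.

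- W = 50: (20,825 + 315×1,275)/(365×1,275) = 422,450/465,375 = **90.8%**.
- W = 35: (7,140 + 330×630)/(365×630) = 215,040/229,950 = **93.5%**.

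Rules 1 and 4 give 0%. With the fix below, rules 2 and 3 also give 0% for AEs with a complete pre-dose stop date.

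**Step 3. Most that one event can move an incidence.** SAP 3.1 makes the pooled Part 1 and Part 2 population (SAF2) primary for safety. With 6 Part 1 subjects added to Part 2 arms of 8, 10 or 20, the SYNB1020 group has 14, 16 or 26 subjects. One subject is then 1/14 = 7.1, 1/16 = 6.3 or 1/26 = 3.8 percentage points. For placebo, or for SYNB1020 in Part 2 alone, the steps are 1/8 = 12.5, 1/10 = 10.0 and 1/20 = 5.0 points. A subject who already has another TEAE adds nothing to overall TEAE incidence.

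**Step 4. The opposite error.** First dose 20 September; AE starts 18 September, worsens on treatment and stops 25 September. Rule 1 excludes it on its start date. With an August start (day missing), the same stop date and worsening on treatment, rule 2 excludes it too. The principle covers worsening as well as occurrence, so these exclusions run against it.

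**The case against.** The strongest defence is that the principle governs and the four rules merely illustrate it. On that view, comparing dates as far as possible already means using a complete stop date. Rule 2 helps this reading a little: it compares the stop month/year with first dosing itself rather than with the month of first dosing. This stands to the extent that rule 2 is less explicit than rule 3. It does not rescue the text. Rule 3 names the year on both sides of its comparison, both rules restrict exclusion to their own tests, and a worst-case approach is for uncertainty, of which there is none here.

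The objections on impact are stronger, and they stand. A reader might infer any of the following, none of which the documents support:

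- **That the primary safety endpoint is inflated.** The endpoint is the nature and frequency of all AEs (Protocol 3.1, SAP 1.2). Any-AE counts do not depend on a TEAE rule.
- **That the comparison between arms is biased.** The rules are identical in both arms, and AE rates are not tested.
- **That related-TEAE tables would fill with pre-dose events.** Those tables need an investigator's judgement of relatedness. Protocol 9.1.2 counts the lack of a reasonable temporal sequence from dosing as grounds for unrelated.
- **That rule 2 misclassifies about 29% over the protocol window.** Counting stop days alone gives (30.4−1)/2 = 14.7 of 51 days. That ignores rule 2's start-month test, which removes many of these events.
- **That TEAE counts must rise overall.** Step 4 shows errors in the other direction, so the net sign is unknown.

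The trigger may also be uncommon. Protocol 9.4 requires start and end dates for every AE. The run-in is inpatient, with direct observation. Protocol 7.2.2 sends signs and symptoms seen before dosing to medical history, although that sits uneasily with recording AEs from consent in 7.2.1.

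**Conclusion.** The inconsistency is real. Rule 3 as written, and rule 2 on its natural reading, can class an AE with a complete pre-dose stop date as treatment-emergent. This contradicts the principle in SAP 4.2.8, rules 1 and 4, and the definition in 4.6.1.

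The shares in Step 2 apply only to AEs with that pattern of missing start date and a complete pre-dose stop date, and they rest on evenly spread start/stop pairs and dosing dates. They are not rates of misclassification among all AEs. The documents do not give the number of AEs affected, so the actual change in any table cannot be calculated.

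The consequence is confined to descriptive TEAE tabulations. Severity: minor.

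**What to change.** In SAP 4.2.8, end rules 2 and 3 with the full stop-date test that rules 1 and 4 already contain. Suggested wording: an AE whose complete stop date precedes the first dose is not treatment-emergent; if the stop date is itself partial, compare it at the precision recorded (month and year, or year).

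In the same edit, align rules 1 to 3 with the principle on worsening, so that an AE that began before dosing but worsened on treatment is not excluded automatically. One way is to state that the worsening is recorded as a new AE with its own start date. Protocol 9.1 already counts exacerbation of a pre-existing condition as an AE. The definition in 4.6.1 should then mention worsening too, since at present it does not.

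The stop-date change costs a phrase in two bullets and a line of derivation code, and it needs no new data. The worsening change adds a sentence to 4.2.8 and one to 4.6.1, plus a check that the case report form can capture it. Both belong before database lock and unblinding, the point by which Protocol Section 10 requires the SAP to be final.

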4.2.9. Visit Windows

Screening procedures must be performed to determine eligibility for enrollment in both Part 1 and Part 2 within 30 days prior to admission to the inpatient facility.

During inpatient monitoring, visit windows are not a concern.

The protocol-specified visit window for the End of Study (EOS)/Discharge Visit to occur is at least 12 hours after completion of the last dose (Day 7); subjects who withdraw early should have this visit within 24 hours of discontinuation of the study drug. The first follow-up visit is specified in the protocol as occurring 7 ± 1 day after the EOS Visit, and subjects will be followed for up to 10 weeks after this first follow-up visit occurs. For continuation of follow-up visits, subjects will be required to provide weekly fecal samples (7 ± 1 day after the follow-up visit) for the first 6 weeks following discharge, and bi-weekly (14 ± 1 day) until the subject has

a negative SYNBI020 fecal test (up to 10 weeks after completion of study). However, all data will be analyzed regardless of visit windows.

Table 1 Visit Windows

Evaluation	Protocol-Specified Interval
Screening	Day -36 to Day -6
Part 1 Inpatient	Day -5 to Day 7
Part 2 Inpatient	Day -5 to Day 7
EOS/Discharge	Day 7 (12 hours post-dose)
Follow-Up	Day 13 to Day 15

4.3. Interim Analyses

After all N=6 subjects are discharged from the clinic following Part 1, safety data will be examined as an informal review (not a formal IA).

A formal, unblinded IA will be performed on the PD2 population (Part 2 only) after at least 16 subjects have completed dosing in Part 2 and have been discharged from the unit, while enrollment may continue, for a possible final sample size of N=20 (N_{CP}). N_{CP} may be adjusted based on actual enrollment just before the IA decision but will not be less than 20.

It is assumed that baseline average daily ammonia is 70 µmol/L, and the placebo group will show a 0 – 10% reduction from baseline, while the desired reduction for the treatment group is 20% versus placebo. Furthermore, the assumed SD of the difference in the means (desired reduction) is 9 µmol/L. Additional assumptions were examined, and the operating characteristics at the IA for these more pessimistic possibilities are shown in Section 6.4.

If the p-value at the IA is < 0.028 the trial could be stopped for efficacy. Otherwise, conditional power (CP) will be computed at the IA for N=16 subjects. This is the probability that the trial will yield a statistically significant reduction in AUC of average daily ammonia change from baseline greater for the treatment group at the end of the trial if the observed difference at the IA is the TRUE underlying difference and the trial is continued to completion with a total of N_{CP} subjects. If this probability is less than 30%, the Safety Monitoring Committee (SMC) could suggest that the trial be stopped for futility. Otherwise, if the CP is less than 90% the sample size will be boosted to target a conditional power of 90%, up to a maximum of 40 patients. If the CP is greater than 90% and the p-value at the IA is greater than 0.028, the trial will end with N_{CP} subjects.

Conditional power for an active dose versus placebo is derived as follows:

$$C_p(\hat{\Theta}) = 1 - \Phi \left\{ \frac{c_2 - B(t)/t}{\sqrt{1-t}} \right\}$$

Parameter	Description
$\Phi\{x\}$	cumulative distribution function for a $N(0, 1)$ random variable
c_2	Adjusted critical cut-off for the final analysis. Assuming that alpha of 0.028 is spent at the interim analysis for one-sided testing, that the total one-sided alpha

	level is 0.05, and that only one IA occurs at the planned information fraction of 0.80 (=16/20), the adjusted critical cut-off is $c_2 = -1.904$.
t	= n/N , where N is the planned total sample size for the treatment arm and for the placebo arm (N=20), and n is the sample size of the IA (16 total).
B(t)	B value, calculated as $Z_n\sqrt{t}$, where Z_n is the Z statistic associated with the linear regression model of observed data on the treatment group versus placebo group at the IA

Because the total number of subjects could potentially be increased in a data-dependent manner, the final analysis does not use the conventional statistic to determine if statistical significance is reached. Instead it uses the weighted statistic proposed by Cui, Hung, and Wang (Cui et al., 1999) (referred to as the “CHW approach”) in which the independent increments of the Z statistic of the 2 stages are combined by pre-specified weights that are based on the planned proportion of total number of subjects at which the IA would be taken if there were no change in the design. In the present case, the study was designed for 30 subjects with an interim analysis when 24 subjects complete the study. Upon further consideration, the interim analysis will be performed when 16 subjects complete the study with a planned total sample size of 20 without adaptation. Details on the operating characteristics can be found in Section 6. Therefore, the planned proportion n is 0.80 (16/20) for stage 1 and 0.2 (4/20) for stage 2 (these values will be adjusted for the actual N and N_{CP} at the IA), and the independent incremental Z statistics for the 2 stages are combined with weights that equal $w_1 = \sqrt{0.80}$ for stage 1 and $w_2 = \sqrt{0.20}$ for stage 2. These weights will remain fixed. They will not be modified based on any changes to the final sample size. The final test statistic under the CHW approach is

$$Z_{CHW} = w_1 Z_1 + w_2 Z_2$$

Where Z_1 is the Z statistic calculated using the IA PD2 population data (i.e., stage 1 data) and Z_2 is the Z statistic calculated using PD2 population data from all remaining subjects not included in IA (i.e., stage 2 data). . Statistical significance is achieved at the final analysis if $Z_{CHW} < c_2$.

The model used for the IA will be a log-scale, linear mixed model with repeated measures with categorical effects for treatment, time (as a categorical variable), and treatment by time and a random effect by subject on the intercept where time will be coded as baseline for pre-dose and treated for both post-dose assessments:

$$\log(AUC_{i,t}) = \beta_t \times \beta_{treatment} + \beta_t + \beta_{treatment} + \eta_i + \epsilon$$

where:

- $AUC_{i,t}$ is the ammonia AUC for subject i at time t,
- β_t is the effect of time (baseline or on-treatment),
- $\beta_{treatment}$ is the effect of treatment (placebo or active),
- η_i is the sample from a normal distribution of the random effect of subject i, and
- ϵ is the log-scale, residual variability.

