6.4. Operating Characteristics of the Interim Analysis

An IA will be carried out at N=12 (with the study ongoing), with a possible sample size re-estimation to a maximum of N=40 subjects, or if no sample size re-estimation, a final sample size of N=16.

The study design was simulated 10,000 times under the assumption that the true AUC of average daily ammonia change from baseline to Day 5/6 shows a 20% reduction (-0.22 on the log scale) in the treatment group versus the control group.

Based on previous data, the standard deviation of average daily ammonia was estimated to possibly be as small as 50% of that of spot ammonia (~13 µmol/L on the log scale). For a more conservative estimate, we assumed that the standard deviation could also be as high as that of spot ammonia (~26 µmol/L on the log scale). Additionally, measurements for healthy volunteers in protocol SYNBI020-CP-001 showed that the total standard deviation was 25 µmol/L and the standard deviation between and within subject was ~20 µmol/L and 15 µmol/L, respectively (64% of the total variation). Thus, a more pessimistic standard deviation from this data will be examined as 29 µmol/L (64% of 36 µmol/L), with a less pessimistic standard deviation as 20 µmol/L.

Analysis of Stage 1 ammonia data indicated a within-subject, log-scale residual standard deviation of 0.1324 from a baseline AUC_{0-24/24} of 64.8 µmol/L (approximately 9 µmol/L).

For an IA at N=16, with overall type I error (alpha) set at 0.10 and efficacy p-value set at 0.028, conditional power (CP) will be calculated to drive the decision about whether to increase the sample size. The following boundaries were set: futility boundary at CP=0.30 and efficacy boundary at < 0.028 (one-sided). If the trial is not stopped for efficacy or futility, then if CP≥90%, the trial will continue to completion with a total of 20 subjects, and if CP <90%, the sample size will be increased

to target a CP of 90% up to a maximum sample size 40. The operating characteristics of the design can be seen in the below table:

	Pessimistic SD #1 SD=26 $\mu\text{mol/L}$	Pessimistic SD #2 SD=29 $\mu\text{mol/L}$	Healthy Volunteer SD SD=20 $\mu\text{mol/L}$	Stage 1 Observations SD=9 $\mu\text{mol/L}$ (log-scale SD = 0.1324)
Probability to stop for futility at N=16	41.91%	47.19%	25.07%	0.13%
Probability to stop for efficacy at N=16	36.62%	33.03%	55.32%	99.12%
Probability of increasing beyond 20 $20 < N \leq 40$	21.47%	19.78%	19.61%	0.75%

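### SAP Section 4.3 prints conditional power with the wrong tail: as written it is the probability of missing significance, which upsets the futility and sample-size rules

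*SAP*

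**What the plan says.** SAP Section 4.3 describes CP as follows: "This is the probability that the trial will yield a statistically significant reduction in AUC of average daily ammonia change from baseline", taking the difference observed at the interim as the true one and N_CP subjects in total. The formula is "C_p(\hat{\Theta}) = 1 - \Phi \left\{ \frac{c_2 - B(t)/t}{\sqrt{1-t", that is, one minus Φ of (c2 - B(t)/t)/√(1-t). Φ is the "cumulative distribution function for a $N(0, 1)$ random variable", and B(t) = Z_n√t.

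The same section fixes the direction of success. It states that "the adjusted critical cut-off is $c_2 = -1.904" and that "Statistical significance is achieved at the final analysis if $Z_{CHW} < c_2". Section 6.4 gives the assumed effect as -0.22 on the log scale. Benefit is therefore negative throughout.

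If the interim p-value is not below 0.028, CP determines what happens next:

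- **CP below 30%:** "If this probability is less than 30%, the Safety Monitoring Committee (SMC) could suggest that the trial be stopped for futility".
- **CP from 30% to below 90%:** the sample size is increased to target 90% CP, up to 40 subjects.
- **CP above 90%:** the trial finishes with N_CP subjects. N_CP is 20 as planned, and it "may be adjusted based on actual enrollment just before the IA decision but will not be less than 20".

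**The concern.** The verbal definition, the negative c2 and the success rule all point to the lower tail, while the formula takes the upper tail. The upper-tail form is right only when benefit is coded positive, c2 is positive and success means exceeding it. The SAP says none of these.

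CP is the only pre-specified driver of the futility suggestion and of any increase to 40. A programmer who follows the text would report a null or harmful trend as more than 90% likely to succeed. Among results that do not stop for efficacy, the more favourable ones would receive the lowest CP.

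**Working it through.** **Inputs.** From SAP Section 4.3: t = 16/20 = 0.80, c2 = -1.904, B(t) = Z1√t (Z1 is the interim Z), success if Z_CHW < c2, interim efficacy if one-sided p < 0.028 (Z1 < -1.911), and CP cut-offs of 30% and 90%. From Section 6.4: the efficacy, futility and increase rates.

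**Derivation.** Under the current trend the final statistic, given the interim, is normal with mean B(t)/t = Z1/√t and variance 1-t. Hence

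P(Z_CHW < c2) = Φ{(c2 - Z1/√t)/√(1-t)}.

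The SAP prints one minus this. The two sum to 1 whatever c2 is. A simulation of w1Z1 + w2Z2 (1,000,000 draws per Z1) agrees with the lower-tail form; at Z1 = -1.0 it gives 0.040, against 0.039 from the lower tail and 0.961 as printed.

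**Example.** For Z1 = -1.5: Z1/√0.8 = -1.677; (-1.904 + 1.677)/√0.2 = -0.507; Φ(-0.507) = 0.306. The printed value is 0.694.

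| Z1 | CP as printed | CP, lower tail |
|---|---|---|
| 0 | 99.999% | 0.001% |
| -1.0 | 96% | 4% |
| -1.5 | 69% | 31% |
| -1.8 | 40% | 60% |
| -1.9 | 31% | 69% |

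**Decision regions when the trial does not stop for efficacy (Z1 ≥ -1.911).**

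| Action | As printed | Lower tail |
|---|---|---|
| Futility (CP < 30%) | Z1 < -1.913: unreachable | Z1 > -1.493 |
| Increase | -1.911 to -1.190 | -1.911 to -1.493 |
| Finish at N_CP (CP > 90%) | Z1 > -1.190 | Z1 < -2.216: already an efficacy stop |

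**No true effect, Z1 ~ N(0,1).** As printed: 88% finish at N_CP, 9% increase, 0% futility. Lower tail: 93% in the futility region, 4% increase.

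**Comparison with Section 6.4.** For each column, take Z1 ~ N(μ,1) with μ chosen so that P(Z1 < -1.911) equals the tabulated efficacy rate. This gives μ = -1.57, -1.47 and -2.04 for SD 26, 29 and 20. The rates for "Probability to stop for futility at N=16" then compare as follows:

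| SD | SAP table | As printed, c2 = -1.904 | Lower tail, c2 = -1.904 | Lower tail, c2 = -1.726 |
|---|---|---|---|---|
| 26 | 41.91% | 0% | 47% | 41% |
| 29 | 47.19% | 0% | 51% | 45% |
| 20 | 25.07% | 0% | 29% | 24% |

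At SD 9 the table gives 0.13%, the printed formula 0% and the lower tail about 0.3% (c2 = -1.904). At c2 = -1.726 the printed formula gives 6% in each of the first three columns, still far from the table.

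The printed formula at c2 = -1.904 would also send 35%, 39% and 20% of trials (SD 26, 29, 20) to finish at 20. The SAP's futility, efficacy and increase rows leave no room for that: 41.91 + 36.62 + 21.47 = 100.00 for SD 26, and the other columns also sum to 100.00. The lower-tail formula gives 0% there at both c2 values.

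**Sensitivity to c2.** The stated inputs (0.028 spent at t = 0.80) do not reproduce -1.904. They give -1.726 for a total alpha of 0.05 and -1.293 for 0.10. That is a separate issue, but it moves the lower-tail figures: CP at Z1 = -1.5 becomes 46% or 80%, and the null futility region 91% or 83%. At c2 = -1.726 the printed futility rule is reachable and flags Z1 from -1.911 to -1.754, the most favourable results that did not stop.

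**The case against.** The algebra is not in dispute; the objections concern consequence and weight.

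- **Inversion is too strong a word.** At the printed values the printed increase zone contains the whole of the correct one, and futility becomes unreachable rather than reversed. This is right for the decision regions. The CP ordering is nevertheless reversed, and only a margin of 0.0017 in Z1 keeps the futility rule unreachable.
- **The extra-subject cost may be smaller.** Going from 16 to 20 is 4 subjects, but enrolment may continue during the interim, so some may already be in. Where no increase is triggered, 0 to 4 is the fairer figure. Futility is also only advisory.
- **A larger N_CP may change c2.** With c2 held at -1.904, N_CP = 21 or 22 makes the printed rule flag Z1 from -1.911 to -1.885 or -1.857. If instead the total alpha implied by -1.904 (about 0.040) is held, c2 becomes -1.928 or -1.949 and the bands shrink to -1.907 or -1.896. They do not vanish.
- **The Section 6.4 match is approximate.** At c2 = -1.904 the lower tail is 4 to 5 points too high in the three larger-SD columns, well beyond simulation error for 10,000 runs (about 0.5 points). Section 6.4 also opens with a different design (12 then 16 subjects). The table rules out the printed formula at c2 = -1.904 but does not show exactly what was coded.
- **A programmer would probably notice.** A CP of 99.999% at zero effect is conspicuous. That lowers the risk but is no reason to leave the formula standing.

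**Conclusion.** The concern holds. The printed formula is the complement of the SAP's own definition of CP, for any c2, and no passage reverses a sign to rescue it. Reversing Z alone does not help: with c2 left at -1.904, CP would be about 1 for every Z of zero or more.

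At t = 0.80 and c2 = -1.904, following the text removes the futility rule and sends 88% of null trials to finish at N_CP as apparent near-certain successes, where the lower-tail rule would put 93% in the futility region. These percentages assume a normal interim Z and will move once c2 is settled; the tail error will not.

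The damage is bounded. The p < 0.028 stop and the CHW test do not use CP, so type I error control is not affected by this point. A missed futility stop costs up to 4 further subjects, and more where an increase is triggered wrongly. That the simulations used the correct tail is an inference. This should be fixed before the interim analysis.

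**What to change.** Replace the formula in SAP Section 4.3 with CP = Φ{(c2 - B(t)/t)/√(1-t)}. Equivalently, code benefit as positive throughout: a positive c2, 1 - Φ in the formula, and success if Z_CHW > c2. Do not mix the two conventions.

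Then confirm that the interim program and the Section 6.4 simulation code use that form. The cost is one formula line, or a consistent change of sign, plus a code check. It needs no patients and no protocol change, and no new simulation for this point unless the check fails.
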